#### Procedures at each visit

Visit 1-Screening visit: Decisional capacity to provide informed consent will be evaluated as much as possible during prescreening as well as at screening visit during informed consent discussion. Capacity will be assessed by asking questions such as: Why is the study being done? What is the study asking you to do? What are the risks of the study? Is the study voluntary? Etc. If in PI's opinion the subject does not have cognitive capacity to provide informed consent, legally authorized representative (LAR) will be required to provide informed consent prior to any study procedures being completed.

Prior to onsite screening visit, the research coordinator sends the consent form to the study participant through email or mail and schedules a time to explain the study and discuss the consent form with the participant via phone Zoom, or other HIPAA-compliant platform. The study participant doesn't need to print the consent or sign the consent. We will finish the consent at on site screening visit with the PI or Sub-I. If the participant is unable to discuss the consent form in advance, consent discussion and review can be done in clinic.

On site screening visit: Consent, demographics, concomitant medications, family medical history, medical history and physical examination (complete physical exam and detailed neurological exam), vital signs, orthostatic blood pressures, tremor evaluation, MDS-UPDRS III, H&Y rating, MOCA, Drug, alcohol and tobacco abuse screening test, safety assessments (as listed in section IV A, including, QUIP-RS, C-SSRS, NPI, Emotional and behavioral dyscontrol short form, Drug abuse-related AEs), EKG and safety labs (including hematology, hemoglobin A1C, Complete metabolic profile and Liver Function Tests), blood cannabis analysis testing, plasma cytokine level tests, serum pregnancy test (for women childbearing potential), and inclusion/exclusion criteria are done. Study participants are instructed not to take cannabis from outside source throughout the study. Tremor constancy and amplitude measure device (Tremor GUI MATLAB package) is dispatched and participants are instructed to use the Tremor GUI MATLAB package to measure their tremors in the clinic and will perform it independently before they leave the clinic. They will measure the tremors at home twice a day (two hours after breakfast dose and two hours after dinner dose) for two days after screening visit and three days prior to the baseline visit.

To reduce in-person clinic visit time, part of the above procedures can be done remotely after onsite screening visit, including: demographics, concomitant medications, family medical history, medical history, safety assessments (C-SSRS, NPI, emotional and behavioral dyscontrol short form, drug abuse related AEs).

Visit 2- Baseline visit: Eligibility confirmation (including tremor evaluation), medical history, concomitant medications collection, formal drug interaction assessment, vital signs, orthostatic blood pressures, brief physical exam, MoCA, MDS-UPDRS, H&Y rating, UDysRS, NMSS, OABSS, tremor constancy and amplitude two hours after taking study drug, TUG test, cognitive assessment battery (including tests of verbal intellectual function, attention, processing speed, executive function, verbal learning and memory, visuospatial memory, speeded verbal fluency, and word retrieval), Anxiety short form, Depression short form, SCOPA-Sleep, ISI, DBAS-16, Pittsburgh Sleep Quality Index, Alertness test, RBDSQ, C-SSRS, IRLS, Fatigue severity scale, Pain intensity and interference short form, PDQ-39, EQ-5D, CGI, PGI, urine drug (THC) test (urine dipstick test), urine pregnancy test (women childbearing potential) and study drug dispensing is done and, if appropriate, randomization. Skin evaluation (Dermatology Intake Form, DLQI, and dermatology

photography) will be done. Alertness test (Stanford Sleepiness Scale) will be done before and three hours after the first dosing was administered at clinic. Tremor evaluations reviewed. Home diary is also dispensed. Participants will pick up PSG equipment and home sleep test instruction and do the home sleep test for up to 14 to three nights before the baseline visit. Participants will complete Morning Daytime Dysfunction questionnaire and sleep diary on the morning after the sleep test. PSG equipment and data collected before or at this visit. Participants take the first dose and are instructed on how to take the medication and how to fill out the diary at home. Participants will be monitored for 2 hours and vital signs and orthostatic blood pressures will be checked at one hour after taking the study drug. Participants are also told to bring in empty, partially used, and unused bottles of study drug at next clinical visit. Participants will be told not to take the study drug on the day of the next visit, as they will take it upon arrival under instruction by study staff. Participants will be given two urine cups, 100 mL each, and will be instructed to collect their urine the morning of the 1.25 mg/kg/day assessment visit. They are asked to fill each cup at least three-quarters full, if possible, and to bring them to the visit (no refrigeration needed). Participants are instructed to measure their tremors at home for three days prior to each dose assessment visit.

Part of the above procedures can be done remotely through Zoom or other HIPAA-compliant platform, between screening and onsite baseline visit: Eligibility confirmation, medical history, concomitant medications collection, NMSS, OABSS, Anxiety short form, Depression short form, SCOPA-Sleep, ISI, DBAS-16, Pittsburgh Sleep Quality Index, Dermatology Intake Form, DLQI, Alertness test, RBDSQ, C-SSRS, IRLS, Fatigue severity scale, Pain intensity and interference short form, PDQ-39, EQ-5D.

Visit 3 (3-4 days, 1.25 mg/kg/day) and Visit 4 (14 (+4) days, 2.5 mg/kg/day), dose assessment visits: On the morning of the visits, participants will collect their urine and bring it to the visits. Study coordinator will collect and store the urine cups in a -80°C freezer until shipment for urinary CBD and metabolites test. Concomitant medications, change in medical history, vital signs, orthostatic blood pressures, complete physical exam, detailed neurological exam, MDS-UPDRS, UDysRS, H&Y rating, tremor constancy and amplitude, NMSS, TUG, Anxiety short form, Depression short form, Emotional and behavioral dyscontrol short form, Fatigue Severity Scale, Pain Intensity and Interference short form, MoCA, RBDSQ, QUIP-RS, C-SSRS, NPI, SCOPA-sleep, ISI, DBAS-16, Pittsburgh Sleep Quality Index, IRLS, OABSS, EQ-5D, PDQ-39, CGI, PGI, blood draw for safety labs (hematology, Complete Metabolic Profile and Liver Function Tests) and blood cannabis analysis, urinalysis, ECG, and urine pregnancy test are done. Study drug compliance check, adverse event check and blinding assessment are done. Participants will take their study drug upon their arrival to the clinic and record the taking time. Blood is drawn for cannabis testing and safety labs three hours after the dose. Participants will be monitored and vital signs and orthostatic blood pressures will be checked at one and three hours (2.5 mg/kg/day dose assessment visit) after taking the study drug. Home diary is collected and reviewed. Urine cups dispensed. In addition to the procedures above, for Visit 3 (3-4 days, 1.25 mg/kg/day), participants are told to bring in empty, partially used, and unused bottles of study drug at next clinical visit. Participants will be told not to take the study drug on the day of the next visit, as they will take it upon arrival under instruction by study staff. Participants are instructed to measure their tremors at home for three days prior to 2.5 mg/kg/day dose assessment visit. Participants will be given the questionnaires of SCOPA-sleep, Anxiety short form, Depression short form, Emotional and behavioral dyscontrol short form, EQ-5D-5L, C-SSRS. Study staff will call the participants on the 3rd to 5th day on 2.5 mg/kg/day to remind them to complete the questionnaires and bring it in at next clinic visit.

For 2.5 mg/kg/day dose assessment visit, participants will pick up PSG equipment and home sleep tests instructions, and perform PSG during the night after at least seven days on the 2.5 mg/kg/day or tolerated max dose, and until (and including) the third night before the visit. Participants will complete Morning Daytime Dysfunction questionnaire and sleep diary on the morning after the sleep test. PSG equipment and data are collected before or at this visit. Participants will also perform full cognitive assessment battery tests and skin evaluation (DLQI and dermatology photography) during this visit. Study drug participants returned are disposed per the SOP at 2.5 mg/kg/day dose assessment visit. Plasma cytokine levels test at 2.5 mg/kg/day visit.

Visit 5-Safety follow up: Vital signs, orthostatic blood pressures, history and complete physical examination, concomitant medications collection, MDS-UPDRS, H&Y rating, UDysRS, NMSS, RBDSQ, QUIP-RS, C-SSRS, NPI, SCOPA-sleep, Anxiety short form, Depression short form, Emotional and behavioral dyscontrol short form, Fatigue Severity Scale, Pain Intensity and Interference short form, IRLS, OABSS, PDQ-39, EQ-5D-5L, adverse event check, urine pregnancy test, and cannabis lab testing are done. Hematology, complete metabolic profile, urinalysis, and EKG will be done if there was a clinically significant change at the high dose evaluation visit compared to baseline visit. The PI will evaluate the participant for signs of withdrawal. On the morning of the visit, participants will collect their urine and bring it to the visit. Study coordinator will collect and store the urine cups in a -80°C freezer until shipment for urinary CBD and metabolites test.

Part of the above procedures can be done remotely 1-3 days prior to or after safety follow up visit: medical history, concomitant medications collection, NMSS, RBDSQ, C-SSRS, NPI, SCOPA-sleep, Anxiety short form, Depression short form, Emotional and behavioral dyscontrol short form, Fatigue Severity Scale, Pain Intensity and Interference short form, IRLS, OABSS, PDQ-39, EQ-5D-5L, adverse event check.

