- To help the participant understand how the study drug affects them we will monitor them in clinic. A validated Alertness Scale will be administered before the dose and again when the blood level is expected to reach peak in three hours.
- We will have the following language in the consent form and will emphasize it verbally: "Whether or not the study drug affects driving ability is not known. You should not drive or operate heavy machinery while taking study drug."

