The study is a randomized, placebo controlled, double-blind parallel design with two treatment arms, each of approximately 2-3 weeks duration. In the 2-3 week treatment phase participants will start study drug and titrate up to the maximum tolerated or targeted dose (2.5 mg/kg/day of CBD). Each participant will have a screening visit, baseline visit within four weeks, 2 dose assessment visits (1.25 mg/kg/day and 2.5 mg/kg/day), and a safety visit (5 visits total). Participants will be evaluated at each dose level for monitoring adverse events, as well as changes in medical history and concomitant medications. Further, in case CBD alters the reliability of self - report, repeated measures will be taken on the third to fifth day at each dose during the clinic visits or at home. The assessments include the assessment of tolerability and symptoms of hepatotoxicity, SCOPA-sleep, Anxiety short form, Depression short form, Emotional and behavioral dyscontrol short form, and EQ-5D-5L. Participants are called 3 and 7 days after stopping the study drug to check for signs of withdrawal. At dose assessment visits, urinary CBD and metabolites will be tested. To maximize compliance the coordinator calls the participant to remind them the next day's clinical visit. To increase compliance with taking study drug, participants will be asked to fill out a diary at home. The diary will be a record of the date and time participants take study drug, dose of the study drug, and adverse and beneficial events. Study drug is dispensed at the baseline visit. Participants will measure their tremor using Tremor GUI MATLAB twice a day (two hours after breakfast dose and two hours after dinner dose) for two consecutive days after screening visit, three consecutive days prior to baseline and each dose assessment visit, as well as during the clinic visits. To evaluate the possible somnolence effect of CBD, participants will be evaluated their alertness before and three hours after they take the study drug at baseline visit.

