- Does not have currently active cancer or is not currently being treated for cancer or inflammatory or atopic disease, listed in Appendix 8. It is not possible to list all such disorders, so the PI will evaluate each subject's medical status and decide if they have any meet that this exclusion criteria.
- No current kidney failure or renal dialysis, chronic respiratory disease requiring daily oxygen, active or treated seizures, and hyperthyroidism.
- No current or in the past seven days any infection, for example common cold or urinary tract infection, again to be at discretion of the PI.

Participants will be consented that the effects of CBD on driving are not known, that some users experience significant sedation but the effects vary among individuals and that participants should not drive while taking the study drug. A limited amount of Uber vouchers will be provided to subjects to assist with transportation needs during the treatment period. Alertness test will be done before and three hours after the first dosing is administered at baseline visit to judge the alertness degree for driving.

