Vital Signs (c)	$\checkmark$	$\sqrt{(n)}$	$\mathbf{N}$	√(p)			$\checkmark$
			(n)				,
Orthostatic Blood Pressures	$\checkmark$	$\sqrt{(n)}$	$\mathbf{N}$	√(p)			$\checkmark$
check	,		(n)				
Height and Weight							
Complete Physical Exam (d)							
Neurological exam (e)			$\checkmark$	$\checkmark$			
Brief physical exam (heart							
and lung auscultation)							
Hematology (f)							
							(m)
Hemoglobin A1C	$\checkmark$						
Complete metabolic profile +							
LFTs (g)							(m)
Plasma cytokines test							
Blood cannabis analysis			1	√ (o)			
			(0)	. (-)			
Urinalysis (h)			$\sqrt{1-1}$				
	,						(m)
Urine drug (THC) test							()
Urinary CBD and					1		 
metabolites levels test (q)							
Urine cups dispense and					1		
urine collection instruction							
	I I				1	1	

ECG (12-LEAD)	$\checkmark$		$\checkmark$		$\checkmark$	
Serum Pregnancy Test (for women childbearing potential)	$\overline{\mathbf{v}}$					(m)
Urine Pregnancy Test (for women childbearing potential)			N			
Assessment of past marijuana use	√					
Drug, alcohol and tobacco abuse screening test	√					
MOCA	$\checkmark$					
Cognitive assessment battery						
Alertness test (Stanford Sleepiness Scale SSS)		$\sqrt{(t)}$ (y)				
MDS-UPDRS part III	$\checkmark$					
MDS-UPDRS (all 4 parts)						
H & Y rating	$\checkmark$					
Schwab & England Daily Activities Scale	$\checkmark$				$\checkmark$	
TUG						
QUIP-RS	$\checkmark$		$\checkmark$			
C-SSRS	$\sqrt{(r)}$	$\sqrt{y}$	$\checkmark$			$\sqrt{(z)}$
RBDSQ		$\sqrt{(y)}$				$\sqrt{(z)}$
NPI	$\sqrt{(\mathbf{r})}$		$\checkmark$		$\checkmark$	$\sqrt{(z)}$
Anxiety short form		√(y)	$\checkmark$		$\checkmark$	$\sqrt{(z)}$
Depression short form		√(y)			$\checkmark$	$\sqrt{(z)}$
Emotional and behavioral dyscontrol short form	√( r)		$\checkmark$	√		$\sqrt{(z)}$
SCOPA-sleep		√(y)		$\checkmark$		$\sqrt{(z)}$
IRLS		$\sqrt{(y)}$				$\sqrt{(z)}$

Fatigue severity scale			√(y)						$\sqrt{z}$
Pain intensity and interference short form			√(y)	$\checkmark$			$\checkmark$		$\sqrt{z}$
Bladder function-OABSS			$\sqrt{y}$	$\checkmark$			$\checkmark$		$\sqrt{z}$
PDQ-39			$\sqrt{y}$				$\checkmark$		$\sqrt{z}$
EQ-5D			$\sqrt{y}$						$\sqrt{(z)}$
CGI							$\checkmark$		
PGI-I									
PGI-C									
Unified Dyskinesia Rating Scale (UDysRS)							$\checkmark$		
NMSS			$\sqrt{y}$				$\checkmark$		$\sqrt{(z)}$
Dermatology Intake Form			$\sqrt{(y)}$						
DLQI			$\sqrt{(y)}$				$\checkmark$		
Insomnia Severity Index (ISI)			$\sqrt{(y)}$				$\checkmark$		

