k. Tremor time percentage and amplitude will be measured by a portable device and laptop. Subject will measure it at home 2 days after screening visit, 3 days before baseline visit, 3 days prior to each dose assessment visit, twice a day (2 hours after breakfast dose and 2 hours after dinner dose), 90 seconds each measurement. Tremor will also be measured at clinic, twice at screening visit, 2 hours after taking study drug at baseline and each dose assessment visit.

1. Treatment assessment visit can occur on 10 (+4) days for each dose.

m. Hematology, chemistry, urinalysis and EKG will be done if there was a clinically significant change at the high dose evaluation visit compared to baseline visit.

n. Subject will be monitored and vital signs will be checked again at before and 1 hour after taking the study drug.

o. Blood drawn will be performed 3 hours after taking the study drug of the clinical visit day.

p. Subject will be monitored and vital signs will be checked at before and 1 and 3 hours after taking the study drug.

q. Clean catch urine collection after taking the study drug. Urine is collected in a 500 mL container and stored in 3-4 small cups (120 mL, fill up to 3/4).

r. Procedures can be done remotely after onsite screening visit

s. Phone call to remind patient to measure tremors at home for consecutive 3 days before the next clinic visit.

t. Alertness test will be done before and 3 hours after taking study drug.

u. Home sleep test will be done after at least 7 days on the max dose and until (including) the 3rd night before 2.5 mg/kg/day dose assessment visit.

v. Morning Daytime Dysfunction Questionnaire and Sleep diary will be done within the first 30 minutes of waking after home sleep test.

w. PSG equipment and data collected on the next day of home sleep test or at baseline or 2.5 mg/kg/day dose assessment visit

x. The sleep study before the baseline visit is to be done from 14 to 3 nights before baseline visit.

y. Procedures can be done remotely, between screening and onsite baseline visit

z. procedures can be done remotely 1-3 days prior to or after safety follow up visit

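### The pre-dose alertness reading is planned in clinic as half of a before-and-after pair around the first dose, but two places also let it be taken remotely on an earlier day

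*Combined protocol and SAP*

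**What the plan says.** Several places plan the alertness test as a pair around the first dose at the baseline visit:

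- Section III, Discussion, gives the purpose and the setting: "To help the participant understand how the study drug affects them we will monitor them in clinic". It then describes one reading ahead of the dose and one at the expected blood peak, 3 hours later.
- Section IV.C.1, Study design: "participants will be evaluated their alertness before and three hours after they take the study drug at baseline visit".
- Section IV.C.1, end of the eligibility criteria, times the second reading "three hours after the first dosing is administered at baseline visit to judge the alertness degree for driving".
- Section IV.C.1, Procedures at each visit, Visit 2: "Alertness test (Stanford Sleepiness Scale) will be done before and three hours after the first dosing was administered at clinic".
- Appendix 1, note t: "Alertness test will be done before and 3 hours after taking study drug".
- Appendix 6, baseline visit table: the first alertness test comes ahead of vital signs and dosing, and the second is marked for 3 hours after the drug.

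Two places also allow the test off site. The Visit 2 remote paragraph includes it in the run "Dermatology Intake Form, DLQI, Alertness test, RBDSQ, C-SSRS, IRLS". In Appendix 1, the row "Alertness test (Stanford Sleepiness Scale SSS)" has one marked cell, tagged both (t) and (y), and note y reads "Procedures can be done remotely, between screening and onsite baseline visit".

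**The concern.** The two instructions do not fit together. A pair meant to show what the first dose does to a participant needs both readings under the same conditions on the same day. Section IV.A describes the SSS as a quick rating of how alert the participant feels, so it captures a passing state. If the first reading comes from another day, the difference between the two mixes any drug effect with ordinary day-to-day variation in sleepiness.

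What is at stake is mainly individual. The stated uses are to help the participant understand how the drug affects them and to judge alertness for driving. This pair is the only scheduled sedation check in the hours around the first dose. The SSS is not repeated at later visits, so a same-day reference that is missed on Day 1 cannot be recovered.

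**Working it through.** No power or error-rate figure bears on this point. The check sets the provisions side by side and adds two pieces of simple arithmetic.

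**1. Which reading can the remote option reach?** The remote window opens after screening and ends at the onsite baseline visit. The first dose is taken at that visit, and the second reading follows it by 3 hours. The second reading therefore cannot fall inside the window. Only the pre-dose reading is affected, which is one of the two scheduled.

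**2. How old could that reading be?** Section IV.C.2, Figure 2 legend, puts screening at Day -28 to Day -1 and the first dose on Day 1, within 4 weeks of screening. The plan's own limit reproduces: 4 weeks × 7 days = 28 days. A remote reading on the screening day could be 28 days old, and one on the following day 27. This is the most the text permits, not the gap to expect.

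**3. Does the entry fit the rest of the remote list?** The alertness test is the only item on it that the protocol times relative to the dose. The other dose-timed baseline measures, vital signs (Appendix 1, note n) and clinic tremor (note k), are not on it. Some listed instruments, such as the PDQ-39 and the Pittsburgh index, look back over the last month and tolerate an earlier date. The SSS does not.

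**4. Is the SSS taken again later?** It is absent from the procedures for Visits 3, 4 and 5 and from the later visit tables in Appendix 6.

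**5. What does the remote option save?** The itemised times in the Appendix 6 baseline table sum to 230 minutes, matching the printed total. The pre-dose alertness test takes 3 minutes: 3 / 230 = 0.013, or 1.3% of the budgeted visit.

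**The case against.** The strongest reply is that the specific text governs. Six places tie the pair to the dose, and Appendix 6 still schedules the pre-dose test in clinic. Against them stand one entry in a list of things that can be done remotely and one tag. The entry may simply have been carried over from the general Visit 2 list, where much the same run of instruments appears. Nothing says that a remote reading replaces the clinic one. Much of this stands: the option is permissive, and harm requires staff to treat a remote reading as the pre-dose reading. But nothing rules that out, and tags (t) and (y) share a single cell.

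Three stronger readings are tempting, and the documents do not support them.

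- *A reader might infer that this is the trial's only before-and-after sedation check.* It is not. SCOPA daytime sleepiness is taken at baseline and at each dose visit. A score above 7 that has risen and is judged problematic returns the participant to the prior dose. The SSS pair is the only check in the hours around the first dose.
- *A reader might infer that a planned analysis is damaged*, because outcome 1.4 in Section IV.A names alertness and compares change from baseline to each dose. The SSS is not scheduled at either dose assessment visit, so no such change can be computed, and Section IV.F does not name it.
- *A reader might infer that the DSMB's request is defeated.* The DSMB asked the PI to consider assessing sedation after the first dose. The 3-hour reading does that, and the remote option cannot touch it.

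**Conclusion.** The inconsistency is real and appears in two places that agree with each other, the Visit 2 text and Appendix 1. Its importance is minor.

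It affects one of two readings and only if the option is used, and the 28-day figure is a ceiling. The 3-hour test stays required. Randomisation would still allow the arms to be compared on the 3-hour readings alone, although that does not restore an individual's own reference. Participants are told not to drive while on study drug whatever they score. Adverse-event checks, the home diary and SCOPA daytime sleepiness still pick up somnolence. No dosing rule, stopping rule or analysis named in Section IV.F uses the SSS, and the primary endpoint and sample size are untouched.

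The conclusion assumes that the SSS is read as a momentary rating, as Section IV.A describes it, and that staff could reasonably take tag (y) as permission to complete the pre-dose reading ahead of the visit. The Visit 2 text says only that the reading comes before the dose. That it comes shortly before is inferred from the order in Appendix 6 and the in-clinic monitoring described in Section III.

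**What to change.** Delete the alertness test from the remote list under Visit 2 in Section IV.C.1, and remove tag (y) from its row in Appendix 1 while keeping tag (t). Both readings are then taken in clinic on Day 1, as the rest of the protocol intends.

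The cost is two deletions. Budgeted visit time does not change, because Appendix 6 already includes the pre-dose reading. A participant who would have used the remote option spends those 3 minutes on site instead.
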